Note: For multi-lumen catheters, the Investigator or designee will designate one lumen only to be used throughout the study for both study drug instillation and assessment of CVAD function. The lumen chosen will be documented and indicated using a study lumen tag to ensure that the same lumen will be used for all study drug instillations and study assessments.

- Subjects who qualify for the study, following completion of all screening assessments, will be administered study medication. **Note that all assessment time points / dwell times have a window of \pm 5 minutes from the time of study drug instillation (0 min).**
- After the first instillation of study drug, the CVAD will remain undisturbed for 30 minutes, at which time an assessment of function will be performed. Assessment of

 Chiesi	Clinical Study Protocol
Clinical Study Code No.: CUSA-081-HEM-01	Version No.: 8.0
EUDRACT No./IND No.: 2019-002124-32/128551	Date: 21 FEB 2023

function will be performed as described in [section 7.2.3](#) by a trained (as deemed by the participating institution) health care professional. Restoration of CVAD function (i.e., treatment success) is defined as follows: the ability to both withdraw at least 3 mL of blood and infuse 5 mL of saline solution.

- If CVAD function has not been restored at **30** minutes after the first instillation of study drug, any aspirated or withdrawn study drug will be re-instilled, and the CVAD will remain undisturbed for an additional 30 minutes and an assessment of function will again be performed at 60 minutes after this first instillation of study drug.
- If CVAD function has not been restored at **60** minutes after the first instillation of study drug, any aspirated or withdrawn study drug will be re-instilled, and the CVAD will remain undisturbed for an additional 30 minutes and an assessment of function will again be performed at 90 minutes after this first instillation of study drug.
- If CVAD function has not been restored by **90** minutes after the first instillation of study drug, the first drug instillation will be withdrawn and discarded, and a second instillation of study drug will be administered within 15 minutes from the withdrawal of the 1st dose. Similarly, subsequent CVAD function will be assessed as described in [section 7.2.3](#) (i.e., after 30 minutes, 60 minutes and then after 90 minutes from instillation of the 2nd dose, if needed).

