Subjects will exit the treatment algorithm when treatment success is achieved at the specified time points, or after assessment of CVAD function 90 minutes following the second instillation of study drug (time point 180 min), whichever occurs first. Once a subject exits the treatment algorithm, assessments of CVAD function are completed for Day 1. In unsuccessful cases, further treatments for restoration of catheter functionality may be provided per the site's standard of care for CVAD. At 180 minutes, or in the case of Early Withdrawal, if treatment success is not achieved, any subsequently administered standard of care and related outcome will be documented.

Subjects will be monitored for AEs (including SAEs and AESIs) during the treatment period (Day 1) from the time the subject is administered the first dose of study drug until the withdrawal of study drug at V1, and for spontaneously reported SAEs and AESIs afterwards up until the Day 30 (± 2 days) follow up assessment.

Concomitant medications and procedures will also be collected as part of the SAE reporting requirements.

At the end of Visit 1, subjects will be discharged with instructions on how to record and report the status of their CVAD during the 30-day follow-up period, including:

- Date of first recurrent catheter re-occlusion (for those with treatment success at V1),
- Date and type of any additional treatment they received for catheter dysfunction, and
- Date of catheter removal or replacement.

7.1.2 Visit 2

The Day 30 (± 2 days) follow-up assessment will occur by phone or in person if the subject has a scheduled clinic visit. Spontaneously reported SAEs, AESIs, and related concomitant medications will be recorded and the status of the CVAD function will be determined by asking the subject to respond to the questions provided at the V1 discharge.

 Chiesi	Clinical Study Protocol
Clinical Study Code No.: CUSA-081-HEM-01	Version No.: 8.0
EUDRACT No./IND No.: 2019-002124-32/128551	Date: 21 FEB 2023

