12.3.6 Safety Variables

Safety analysis will be based on SS set.

Adverse Events

All adverse events starting from the time the subject is administered the first dose of study drug on Day 1 until the withdrawal of study drug will be classified as treatment emergent adverse event (TEAE). The number of subjects who experience at least one TEAE, ADR, SAE, serious related TEAE, TEAE leading to study withdrawal, TEAE leading to death, and AESI (as defined in [Section 10.1](#)), will be summarized. Post-treatment adverse events during the 30-day follow up period will be summarized. Summaries will be presented by actual treatment arm and by system organ class and preferred term as the number and percentage of subjects having at least one event and the total number of events.

 Chiesi	Clinical Study Protocol
Clinical Study Code No.: CUSA-081-HEM-01	Version No.: 8.0
EUDRACT No./IND No.: 2019-002124-32/128551	Date: 21 FEB 2023

For AESIs, the percentage of subjects who experienced AESI and associated exact binomial 95% confidence interval will be provided in the summary.

All adverse events will be listed.

Vital signs

Vital signs (systolic and diastolic blood pressure, heart rate) will be summarized by means of descriptive statistics. Mean, min, max and standard deviation of the observed values will be presented, in addition to being listed.

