### 10.2 Adverse Events

An AE will be classified as follow (See also Section 7.3):

- Pre-treatment AE: if it starts before the first study drug intake (AE onset date/time < date/time of first study drug intake);
- Treatment emergent AE (TEAE): if it starts on or after the first dose of study drug intake up to the end of the treatment period (date/time of first study drug intake ≤ AE onset date/time ≤ end date/time of the treatment period);
- Post-treatment AE: if the onset date is after the end of the treatment period (AE onset date/time > end date/time of the treatment period).

The treatment period is defined as the period between first study drug administration and the following end:

- For subjects who completed the treatment period without achieving treatment success, the end of the treatment period will be the date/time of the 180-minutes CVAD assessment;
- For subjects who achieving treatment success, the end of the treatment period will be the date/time of the CVAD assessment where patency is achieved;
- For subjects who discontinued the treatment due to AE or death, the end of the treatment period will be the start date/time of the relevant event and the event will be considered as treatment emergent;
- For subjects who discontinued the treatment due to other reasons, the end of the treatment period will be the date/time the last CVAD assessment performed.

An ADR is an AE related to study medication. A serious ADR is a SAE related to study medication.

A severe AE is an AE with severe intensity. Refer to Section 7.3 for missing severity.

An AE leading to discontinuation is an AE with action taken with study drug equal to “Drug Permanently Withdrawn”.

An AE leading to death is an AE with outcome equal to “Fatal”.

Two AEs with the same PT and classified in the same category (pre-treatment AE, TEAE or post-treatment AE) will be considered as two different events when calculating the “number of events” in the tables.

Pre-treatment AEs, TEAEs and post-treatment AEs will be presented separately. Pre-treatment AEs will be presented in the listings only.

A summary table displaying the number and the percentage of subjects experiencing at least one TEAE, serious TEAEs, ADRs/drug-related TEAE, serious ADRs, severe TEAEs, TEAEs leading to study drug discontinuation, TEAE of special interest (See Section 10.2.1) and TEAEs leading to death, as well as the number of events, will be presented by actual treatment group.

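### For subjects who stop treatment early, SAP 10.2 ends the treatment-emergent window at a different point from Protocol 12.3.6, without declaring it in SAP 12, so some events that start with drug still in the catheter are classed as post-treatment

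*SAP*

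**What the plan says.** Protocol 12.3.6 has one rule for all subjects. Adverse events from the first dose "until the withdrawal of study drug will be classified as treatment emergent adverse event (TEAE". Protocol 7.1.1 uses the same limits for AE monitoring on Day 1: "from the time the subject is administered the first dose of study drug until the withdrawal of study drug at V1". Protocol 10.1 uses them again for the first part of AESI collection.

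SAP 10.2 defines a treatment period with four possible ends, and none is worded as drug withdrawal. Two of them concern early stopping:

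- Stop because of death or an AE: "the end of the treatment period will be the start date/time of the relevant event and the event will be considered as treatment emergent".
- Stop for any other cause, that is, subjects who "discontinued the treatment due to other reasons, the end of the treatment period will be the date/time the last CVAD assessment performed".

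Anything later falls in the next class: "Post-treatment AE: if the onset date is after the end of the treatment period".

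SAP 12 lists three changes from the protocol: the analysis set for non-inferiority, the cancelled futility analysis, and the basis of the Per-Protocol Set. The treatment-emergent window is not among them.

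**The concern.** Treatment emergence should follow exposure, and here exposure is the time the drug sits in the lumen. A CVAD assessment does not necessarily end it. After a failed check at 30 or 60 minutes, "any aspirated or withdrawn study drug will be re-instilled, and the CVAD will remain undisturbed for an additional 30 minutes". The onset of an AE does not end it either: Protocol 4.4 describes serious bleeding in a critical location as occurring first, with the drug withdrawn from the catheter afterwards. Both SAP end points can therefore come before the end of exposure, and an event starting in between is a TEAE under the protocol but post-treatment under the SAP.

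At stake are the outputs in SAP 16.1 that cover treatment-emergent events only: the overview (Table 14.3.1.2.1), the two AESI tables (14.3.2.1, with exact binomial intervals, and 14.3.2.2) and the fatal-TEAE table (14.3.2.3). The table list has no post-treatment counterpart for any of these.

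**Working it through.** The documents give no figure to reproduce. The check applies both rules to the dosing timeline and counts dwell minutes after the SAP end point.

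Inputs:

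- Checks at 30, 60 and 90 minutes after each instillation, labelled 120, 150 and 180 for the second dose, each with a window of ±5 minutes (Protocol 7.1.1 and Table 7).
- Re-instillation after failed 30- and 60-minute checks (Protocol 7.1.1).
- After a failed 90-minute check, "the first drug instillation will be withdrawn and discarded, and a second instillation of study drug will be administered within 15 minutes" of that withdrawal (Protocol 7.1.1).

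Assumptions: no extra assessment is made when the subject stops, and the drug is removed at the stop.

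**Stops for reasons other than AE or death**

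| Subject stops | SAP end of window | Dwell outside window, nominal | At window extremes |
|---|---|---|---|
| Before the 30-minute check | Undefined, or the pre-dose screening assessment | up to 30 min | 30 + 5 = 35 min |
| Between the 30- and 60-minute checks | 30-minute check | 60 − 30 = up to 30 min | (60 + 5) − (30 − 5) = 40 min |
| Between the 60- and 90-minute checks | 60-minute check | 90 − 60 = up to 30 min | (90 + 5) − (60 − 5) = 40 min |
| At the failed 90-minute check, no second dose | 90-minute check | about 0 | about 0 |
| After dose 2, before the 120-minute check | 90-minute check, which precedes dose 2 | all dose 2 dwell so far, up to 30 min | 30 + 5 = 35 min |
| Between the 120- and 150-, or the 150- and 180-minute checks | Last check | up to 30 min | 40 min |

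The last row assumes that the re-instillation steps also apply to the second dose. Protocol 7.1.1 says function is assessed similarly after it, but does not repeat those steps.

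Example: syringe 2 is given at 100 minutes, an AE starts at 105, and the subject stops at 120 before the next check. The SAP window closed at 90, so the AE is post-treatment. All 120 − 100 = 20 minutes of dose 2 dwell lie outside the window. Under the protocol the AE is a TEAE.

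**Stops for an AE or death**

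The gap runs from onset of the triggering event to drug removal. The documents give no duration for it. Example: the triggering AE starts at 10 minutes, a separate AE at 40, and the drug is removed at 55. The triggering AE is treatment emergent. The one at 40 is post-treatment under the SAP, with 55 − 10 = 45 minutes of dwell outside the window, and a TEAE under the protocol.

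**With the protocol end point**

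Uncovered dwell is 0 minutes in every row.

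**Number of subjects**

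This cannot be computed, because neither document gives a rate of early treatment stopping. The allowance of 841 − 800 = 41 randomized subjects concerns completing the study through Day 30, so it does not measure stopping within Visit 1.

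**The case against.** The best case for the SAP is that little changes in practice, and several parts of it stand.

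- The AE that causes the stop is expressly kept as treatment emergent. A serious bleed during dwell would normally lead to drug withdrawal and so be that AE. Only a further, separate event can move. Where several AEs led to withdrawal, the SAP does not say which onset counts.
- Moved events are reclassified, not lost. SAP 16.1 has post-treatment tables by system organ class and preferred term, including serious, severe and drug-related events. Listing 16.2.7.11 shows every post-treatment AE with its AESI category.
- SAP 7.10 foresees early discontinuation data. An assessment made at the moment of stopping would close most of the gap.
- SAP 7.3 puts AEs with incomplete times into the treatment-emergent class first. That protects only events whose own date or time is incomplete; an AE with a known onset gets no help from it.

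SAP 10.2 also says its tables will be repeated for post-treatment events, which could be read to include fatal events. The table list in SAP 16.1 does not carry that through, nor does it provide a post-treatment AESI table or overview.

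A reader might go further and infer that the rule hides events in the very subjects most likely to have them. The documents do not support this: the last-assessment rule covers stops for causes other than AE or death, and nothing says those subjects have more events. A reader might also infer that no AE can be treatment emergent in a subject who stops before the 30-minute check. That holds only if the screening check counts as the last assessment. The SAP does not say so, and undefined is the fairer description.

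**Conclusion.** The two documents define the end of the treatment-emergent window differently for early stoppers, and SAP 12 does not declare it. The stated SAP rule classes some events during exposure as post-treatment. Per affected subject, the dwell outside the window is nominally up to about 30 minutes for stops for other reasons (35 to 40 at the window extremes), and includes all second-dose dwell for a stop before the 120-minute check. It is about zero for a stop at the failed 90-minute check without a second dose, so not every early stopper is affected. For AE stops it equals the unreported time from onset to drug removal.

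The consequence is confined mainly to the TEAE overview, the AESI tables and the fatal-TEAE table. With few stops expected in a visit of about three to four hours, the number of subjects is probably small, but that is a judgement. The mismatch is certain from the text; its effect on results is not. It should be corrected because AESI counts may be low, so one moved major bleed would be visible in the table and its exact interval.

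**What to change.** Replace the two discontinuation bullets in SAP 10.2 with one rule: for subjects who discontinue treatment for any reason, the treatment period ends at the date/time study drug was withdrawn from the catheter, and never earlier than the last instillation, the last CVAD assessment, or the onset of the AE leading to discontinuation. This also settles the case with no post-dose assessment.

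None of the planned listings shows a drug-withdrawal time, although SAP 7.12 says all eCRF data will be listed, so it may not have been captured. Where it is missing, class Day 1 AEs with onset after the first dose as treatment emergent, as a stated conservative rule in line with the ordering in SAP 7.3. Record the rule in SAP 12, noting that this fallback may run slightly beyond the protocol window. It should not be assumed that the protocol end point can be derived exactly from the data held.

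The cost is a few lines of text and one derivation in the AE dataset, plus a slightly longer window for a few discontinued subjects than for those who completed or succeeded. SAP 12 describes database lock and unblinding as still to come, so the change can be made blind. If the sponsor prefers the present rule, the minimum is to declare and justify it in SAP 12 and define the end point when no post-dose assessment exists.

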### 10.2.1 Adverse Events of Special Interest (AESI)

AESI include the following:

- Major bleeding (defined as severe blood loss [ $>5$  mL/kg] or blood loss requiring transfusion or causing hypotension requiring use of inotropic agents);
- Embolism;
- Thrombosis;
- Catheter related blood stream infections (CRBSI).

The number and percentage of subjects who experienced treatment emergent AESI and associated exact binomial 95% confidence interval for proportion will be provided in the summary. The number and percentage of subjects who experienced treatment emergent AESI by AESI category will be also summarized.

All AESI will be listed.

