Hospitalization refers to a situation whereby an AE is associated with unplanned formal overnight admission into hospital, usually for purpose of investigating and/or treating the AE. Hospitalization for the treatment of a medical condition that occurs on an “elective” or “scheduled” basis or for a pre-existing condition that did not worsen during the study should not necessarily be regarded as an AE. Complications that occur during the hospitalization are AEs. If a complication prolongs hospitalization, the event is an SAE. Emergency room visits that do not result in a formal admission into hospital should be evaluated for one of the other seriousness criteria (e.g., life-threatening; persistent or significant disability or incapacity; medically significant).

- **Results in persistent or significant disability or incapacity.**

The term significant disability should be viewed as any situation whereby an AE has a clinically important effect on the subject’s physical or psychological well-being to the extent that the subject is unable to function normally.

- **Is a congenital anomaly or birth defect**
- **Is a medically significant adverse event**

This criterion allows for any situations in which important adverse events/reactions that are not immediately life-threatening or do not result in death or hospitalization may jeopardize the subject’s health or may require intervention to prevent one of the above outcomes.

Examples of such events are intensive treatment in an emergency room or at home for allergic bronchospasm; blood dyscrasias or convulsions that do not result in hospitalisation; or development of drug dependency or drug abuse.

Medical and scientific judgment should be exercised in deciding whether an event is serious because medically significant.

Any suspected transmission via a medicinal product of an infectious agent is also considered a serious adverse reaction.

B. Non-Serious Adverse Event/Non-Serious Adverse Drug Reaction is an adverse event or adverse drug reaction that does not meet the criteria listed above for a serious adverse event/serious adverse drug reaction.’

C. Adverse Events of Special Interest (AESI): Adverse Events of Special Interest (AESI) will be collected from the time the subject is administered the first dose of study drug on Day 1 until the withdrawal of study drug (V1), and if spontaneously reported afterwards up until the 30 days ± 2 days follow up assessment

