10.9 Reporting Serious Adverse Events and Adverse Events of Special Interest

The Investigator must report all Serious Adverse Events (SAEs) and all Adverse Events of Special Interest (AESIs) to the [REDACTED] Safety Contact listed below within 24 hours of awareness. The information must be sent by providing the completed SAE/AESI form. The [REDACTED] Safety Contact will report all information to Chiesi Global Pharmacovigilance, the Clinical Project Manager and the Clinical Research Physician.

Name and Title	E-mail
[REDACTED] Safety Contact	[REDACTED]
Chiesi Safety Contact	[REDACTED]

- The reporting period for SAEs from the investigator site is from the time of subject's signature of informed consent and until the subject's study participation ends. After this date, even if no active monitoring of subjects is required, SAEs occurring to a subject should be reported if the investigator becomes aware of them.
- Reporting of AESI is from the time the subject is administered the first dose of study drug on Day 1 until the 30 days \pm 2 days follow up assessment.
- Up to the closure of the site, SAE reports should be reported to the [REDACTED] Safety Contact. New serious adverse events occurring after the site is closed should be reported directly to the Chiesi Safety Contact.
- The SAE and AESI information should also be completed simultaneously in the adverse event page of the case report form (CRF).

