**Adverse Events (AEs): Missing/Incomplete Date**

In case of missing or incomplete date/time not directly allowing allocation to any of the category of AEs, a worst-case allocation will be done according to the available parts of the start and the stop dates/times. The AE will be allocated to the first category allowed by the available data, according to the following order:

1. Treatment emergent;
2. Post-treatment;
3. Pre-treatment.

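### AESIs are collected to Day 30, but every planned AESI percentage and confidence interval covers only the treatment-emergent window of Visit 1; one added table by category and arm would close the gap

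*SAP*

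**What the plan says.** **Collection.** Protocol 10.1 collects AESIs from the first dose until study drug is withdrawn at Visit 1, "and if spontaneously reported afterwards up until the 30 days" ± 2 contact. Protocol 10.9 gives the same span without mentioning spontaneous report: "Reporting of AESI is from the time the subject is administered the first dose of study drug on Day 1 until the 30 days" ± 2 contact.

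**Analysis.** SAP 10.2.1 provides "The number and percentage of subjects who experienced treatment emergent AESI and associated exact binomial 95% confidence interval", and a breakdown by AESI category with the same limit. Protocol Section 9 and SAP 4.2 both name the safety variable as treatment-emergent AESIs. The AESI sentence in Protocol 12.3.6, which asks for a percentage and an exact interval, does not carry that limit.

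**The window.** Protocol 12.3.6 defines treatment emergent as onset between the first dose and withdrawal of study drug. SAP 10.2 makes this operational. "For subjects who achieving treatment success, the end of the treatment period will be the date/time of the CVAD assessment where patency is achieved". Without success, it ends at the 180-minute assessment.

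**Post-treatment tables.** SAP 10.2 says its tables will be repeated for post-treatment events.

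**The concern.** The four AESI categories are the harms the trial singled out, and two of them, thrombosis and catheter-related infection, can plausibly appear days after an instillation. The protocol collects them for a month, yet the only AESI proportions with intervals describe the first minutes to hours. A reader who wants major bleeding, embolism, thrombosis or bloodstream infection by arm over the collection period must filter a listing and count.

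The window also depends on the efficacy outcome. Subjects whose catheter opens early stop contributing to the AESI tables early, while failures are counted to the 180-minute assessment. Arms with different success rates are therefore compared over different lengths of time.

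**Working it through.** The plan states no AESI rate and no figure on this point, so there is nothing to reproduce. The check compares outputs, measures the window, and counts table shells.

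**1. What each output covers (SAP 16.1 and 16.2)**

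- Table 14.3.1.2.1 (AESI row), Table 14.3.2.1 (by category, exact CIs) and Table 14.3.2.2 (by category and preferred term): treatment emergent only.
- Listing 16.2.7.8, the dedicated AESI listing: treatment emergent only.
- Tables 14.3.1.2.11 to 14.3.1.2.18: post-treatment events by arm, by system organ class and preferred term, with no AESI grouping and no interval.
- Listing 16.2.7.11: post-treatment events by subject. Its layout follows Listing 16.2.7.2, which has an AESI category column.

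So a later AESI is tabulated by preferred term and listed with its category, but no table counts subjects by AESI category and arm after the window closes.

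**2. Length of the window**

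The shortest window for a success is the first assessment, at 30 minutes. For the longest, the second dose need not follow the first immediately: "a second instillation of study drug will be administered within 15 minutes from the withdrawal of the 1st dose" (Protocol 7.1.1). The nominal 180-minute assessment can therefore fall at 90 + 15 + 90 = 195 minutes. A 30-day period has 30 × 1,440 = 43,200 minutes.

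- 30 / 43,200 = 0.07%; 195 / 43,200 = 0.45%.
- With the ±5-minute assessment windows and the ±2-day contact window: 25 / 46,080 = 0.05% and (95 + 15 + 95) / 40,320 = 205 / 40,320 = 0.51%.

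Two other endings apply to discontinuations. Where an adverse event or a death stops treatment, SAP 10.2 states: "the end of the treatment period will be the start date/time of the relevant event and the event will be considered as treatment emergent". Where treatment stops on any other ground, it states: "the end of the treatment period will be the date/time the last CVAD assessment performed".

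Some later events can enter the window through incomplete dates or times. SAP 7.3 says "The AE will be allocated to the first category allowed by the available data, according to the following order", and treatment emergent comes first in that order.

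**3. Dependence on outcome**

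An AESI starting 45 minutes after the first dose is post-treatment if patency was found at 30 minutes, and treatment emergent if it was not.

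For a rough average by arm, weight the nominal end times by assumed success rates. Let c30, c60 and c90 be cumulative success by 30, 60 and 90 minutes:

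mean = 30·c30 + 60·(c60 − c30) + 90·(c90 − c60) + (1 − c90)·L,

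where L runs from 120 minutes (all remaining subjects succeed at the next assessment) to 180 minutes (none does before the last).

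- CUSA-081, rates from the open-label study in Protocol 1.3 (66.9% at 30, 88.5% at 60, taken flat to 90): 47 to 54 minutes.
- CUSA-081, 75% at 90 minutes (Protocol 12.1) with the historical alteplase time course (51.9%, 59.6%, 67.3%, the middle value interpolated): 60 to 75 minutes.
- Alteplase at those historical rates: 66 to 86 minutes.
- Placebo, 20% at 90 minutes, any timing of the successes: 102 to 162 minutes.

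Placebo would be observed for about 102 / 75 = 1.4 to 162 / 47 = 3.5 times as long as CUSA-081. These are outer limits: they pair opposite values of L across arms or rest on the most favourable CUSA-081 rates.

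**4. What an interval with no events would mean**

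The exact 95% upper limit with zero events is 1 − 0.025^(1/n). At the planned arm sizes this gives 0.78% (n = 473), 6.72% (n = 53) and 1.16% (n = 315). In the planned tables these limits would describe the Visit 1 window, not 30 days. The study stopped early (SAP Section 12) and the achieved numbers are not given, so the actual limits will differ.

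**5. Shell count**

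Treatment-emergent tables by organ class and preferred term: 14.3.1.2.2 to 14.3.1.2.10 (9) plus 14.3.2.3 (1) = 10. Post-treatment: 14.3.1.2.11 to 14.3.1.2.18 = 8. The two without a counterpart are AEs leading to treatment discontinuation and AEs leading to death. If the promised repeat also covers the overview table, which the text leaves open, three are missing.

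**The case against.** The strongest reply is that the SAP does what the protocol declared. The Protocol Outline, Protocol Section 9 and SAP 4.2 all specify treatment-emergent AESIs. Protocol 12.3.6 sets the short window itself, and separately asks for follow-up events to be summarised. The SAP delivers both. Subjects leave the treatment algorithm once function is restored, so any on-treatment window must be shorter for successes, and the 45-minute event is still tabulated, among post-treatment events. This stands.

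It is also fair that pooling first dose to Day 30 mixes two kinds of ascertainment and includes later standard-of-care treatment after failure, whereas SAP 10.2 presents the periods separately. That argues for showing the periods side by side, not for omitting the later one.

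The missing shells are clerical. SAP 10.2 already promises the tables, the discontinuation table would be nearly empty because the event that ends treatment is treatment emergent by rule, and fatal events fall within the serious post-treatment Table 14.3.1.2.13. This stands too, although fatal events are not separated there and the death listing (16.2.7.10) is treatment emergent only.

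What the reply does not meet is that tables by organ class do not group events into the four AESI categories. The plan yields no proportion with an interval for those categories beyond Visit 1.

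**Conclusion.** The gap is real, and it is one of presentation. For subjects who complete treatment, all AESI proportions with intervals rest on about 30 to 195 minutes of a collection period of about 30 days, with a cut-off that depends on treatment success. No data are lost, efficacy is unaffected, and no between-arm safety test is planned.

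Three stronger readings are tempting, and the documents do not support them:

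- *The SAP departs from the protocol.* It agrees with the declared safety variable and the protocol's own treatment-emergent definition. The unrestricted AESI sentence in Protocol 12.3.6 makes the protocol's wording uneven, but does not establish a departure.
- *More than 99% of AESIs go unreported by category.* The 0.07% to 0.45% is a share of clock time, not of events. AESIs may cluster early, and with no AESI rate in the documents the number outside the window cannot be estimated.
- *Later AESIs or deaths disappear.* They are in the post-treatment tables and in Listing 16.2.7.11.

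The window lengths rest on the stated schedule and tolerances. The comparison of mean windows by arm rests on assumed success rates.

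**What to change.** Before unblinding:

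1. Keep the treatment-emergent AESI tables. Add one table by actual arm giving subjects with any AESI and with each AESI category, with exact 95% CIs, in separate columns or panels for post-treatment onset and for first dose through the Day 30 contact.
2. Footnote that subjects without success may have received standard-of-care treatment after Visit 1, which affects the comparison with placebo.
3. State in the same footnote how AESIs after Visit 1 were ascertained, once the protocol is reconciled. Sections 7.1.1 and 10.1 limit collection after Visit 1 to spontaneous reports, while 10.8 requires routine open questioning until participation ends.
4. As a minor table-list correction, add the post-treatment shells for AEs leading to death and to treatment discontinuation. Say whether the overview table is also to be repeated, and add its shell if so.

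The cost is one table and two or three shells from data already collected, with no change to efficacy. The downside is that the 30-day proportion may undercount if reporting after Visit 1 was passive, which the footnote should say.
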